#### **Post-intervention interview (M4M condition only)**

Participants in the M4M condition will also complete a semi-structured interview via video conferencing software (WebEx or Zoom) with a member of the research team. A copy of the interview guide is enclosed. Interviews will be conducted virtually to prevent illness exposure (e.g., COVID-19) and to make participation more convenient for patients. We expect that each interview will take 30-45 minutes. We will record the interview to capture each participant's comments verbatim, and then transcribe interviews for analysis.

All efforts will be made to have each M4M participant complete an interview. The study staff will reschedule an interview up to 4 times before considering a participant incomplete. Study staff will attempt to remain in contact with via phone, text, or email with the participants.

#### **Intervention website use data:**

Working with the MLC web development team, the research team will obtain backend data from the intervention website and will link these data to participants' other study data using their email address. These data will include every action participant took to interact with the intervention website, such as logging in, viewing meals, ordering meals, viewing resources (e.g., recipes, exercise videos), and the date and time spent doing each action.

#### **Medical record abstraction:**

Clinical outcomes will be abstracted from the electronic health record by study staff at UConn Health or Maternal Fetal Medicine Fellows at St. Francis Hospital and Hartford Healthcare Women's Ambulatory Health Services clinic. Data will be abstracted into a REDCap database. Data abstracted from the clinical record will include:

- Maternal characteristics (body mass index, age, gravidity, parity) and preexisting medical conditions (e.g., hypertension, thyroid disease) and medications taken to treat preexisting medical conditions.
- GDM management outcomes (weekly capillary blood sugar readings, use of insulin or other medications for glycemic control)
- Pregnancy outcomes (preterm delivery < 37 weeks, preeclampsia or other hypertensive disorders, fetal growth restriction, hemorrhage, transfusion, chorioamnionitis, cesarean delivery, wound infection, low Apgar score (<7 at 5 minutes), small for gestational age, meconium aspiration, large for gestational age, macrosomia, and total gestational weight gain
- Neonatal/infant outcomes include intrauterine fetal demise/stillbirth, fetal growth restriction, and macrosomia. Adverse newborn outcomes include high c-peptide values, birth trauma, hyperbilirubinemia, hypoglycemia, neonatal demise, low Apgar score (<7 at 5 minutes), small for gestational age, meconium aspiration, large for gestational age, NICU admission, IV glucose treatment, respiratory distress syndrome, necrotizing enterocolitis, intraventricular hemorrhage, neonatal infection, and neonatal micronutrient deficiencies. Identification of large for gestational age (via birth weight and ponderal indices) will be collected and will use growth standards that account for race and Hispanic ethnicity.

### **Feasibility Outcomes**

Below we detail our feasibility outcomes, how they will be measured, benchmarks for assessing feasibility, and how we will use resulting information to inform the design of the efficacy trial.

Feasibility outcome	How measured	Benchmark	How information will inform design of efficacy trial
Recruitment	Recruitment rates will be calculated from the number of patients approached and reasons for ineligibility and	At least 75% of the patients screened as eligible should be recruited but the trial will not be feasible if recruitment uptake is 50% or less; we anticipate	We will compare yield from different recruitment approaches and finalize our approach for the efficacy trial based on the most effective and efficient approaches. We will examine whether any eligibility criteria are excluding an inordinate proportion of otherwise eligible women, and if so, reassess

	non-participation.	recruiting 4-5 participants per month	scientific and practical necessity of each eligibility criterion. If recruitment rates are lower than expected, we will adjust recruitment timelines or modify our recruitment strategy or consider a second clinical site.
Retention	Proportion of participants who complete any aspect of the follow-up assessment	≥80% retention in each arm with 65% or less retention indicating that the main trial is not feasible	If retention is lower than expected, we will explore reasons for drop-out and modify the protocol to address these challenges.
Receipt of intervention	Records of # meals ordered per week and # of produce bags ordered per week; Records of # of exercise sessions	≥80% food budget spent based on \$266 per week ≥80% completed sessions with exercise trainer based on number of sessions eligible to complete	If compliance with meal ordering and completion of exercise sessions does not meet our targets, we will explore alternative strategies for increasing compliance with the interventions and modify the protocol to address these challenges. We will also describe engagement with other aspects of the intervention website using back-end data from the intervention website and qualitative feedback from post-intervention interviews with participants randomized to the M4M condition.
Intervention acceptability	Participants in both conditions will be asked if they would participate again if they	≥80% of participants indicate “likely” or “very likely” on	We will interview participants in the M4M condition who have completed the trial (after delivery) to understand feasibility and acceptability issues and use their feedback to modify study

	had GDM in the future and if they would recommend the program to a friend with GDM (5-item Likert scales of likelihood) 	both measures of acceptability	procedures or intervention materials before moving to a full-scale efficacy trial. We will also examine responses to addition questions assessing frequency of use of and ratings of helpfulness and relevance of other aspects of the M4M intervention.
--	--	--------------------------------	--

### Subject Compensation

Participants randomized to the UC condition will be compensated for their time to complete the baseline and follow-up assessments and the completion of ASA-24 dietary recall.

- UC participants will receive a \$10 gift card (i.e., Amazon) for completion of the baseline assessments.
- UC participants will receive a \$20 gift card (i.e., Amazon) for completion of follow-up assessments.
- UC participants will receive a \$10 gift card (i.e., Amazon) for each completed ASA 24 diet recall at baseline and follow-up assessment timepoints. UC participants can receive up to \$60 for completing all the ASA-24 diet recalls.
- UC participants will receive up to \$90 in gift cards for their participation in the study.

Participants randomized to the M4M condition will be compensated for their time to complete the baseline and follow-up assessments and the completion of the ASA-24 dietary recall.

- M4M participants will receive a \$10 gift card (i.e., Amazon) for completion of the baseline assessments and a \$20 gift card for follow-up assessments. To receive the gift card at follow-up participants in the M4M condition must complete both the online survey and interview.
- M4M participants will receive a \$10 gift card (i.e., Amazon) for each completed ASA 24 diet recall at baseline and follow up assessment timepoints. M4M participants will receive up to \$90 in gift card reimbursement for their participation in the study.

M4Ms participants will also receive a weekly food budget of \$266 per week to select GDM prepared meals and produce bags for up to 11 weeks (up to a total of \$2926 food credits) and will be allowed to keep the activity tracker and Wi-Fi scale.

## Risks

### Risks to Subjects

The possible risks of this study include a food-borne illness, injury while being physically active, episodes of hypoglycemia, possible discomfort from completing questionnaires, and breach of confidentiality. Study activities do not differ from typical everyday activities and risks of pregnant persons with GDM (e.g., eating meals prepared outside of their home such as from restaurants, interacting with others online, using a mobile app) and/or activities done or recommended clinically and in line with national recommendations for diet and exercise during the pregnancy (e.g., eating a ADA compliant diet, regular exercise, measurement of weight) and thus does not pose more than minimal risk/slight increase over minimal risk.

Protection against risks:

Physical Risks:

Meals will be prepared within commercial kitchens by chefs affiliated with My Local Chefs (MLC). The commercial kitchens have been inspected and certified in the prevention of the spread of food borne illnesses by the State of Connecticut Department of Public Health. Participants who receive prepared meals from MLC will be instructed to keep prepared meals refrigerated or freeze to prevent food born illness. Participants will also be provided instructions on how to appropriately reheat the meal for consumption.

Participants must have medical clearance from their prenatal care provider including confirming their ability to engage in physical activity. Medical conditions preventing the increase of physical activity will be exclusionary. We will obtain medical clearance from a member of each participant's prenatal care provider including clearance to participate in physical activity. Research staff will provide additional education about safely engaging in physical activity during pregnancy, and warning signs to watch for. Participants will be encouraged to listen to their bodies during exercise, and to stop exercising if they experience unexpected levels of discomfort or warning signs for physical activity during

pregnancy. Participants who experience discomfort will be asked to meet with their PCP /OBGYN prior to returning to physical activity.

Participants will be educated by study staff to measure their capillary blood sugar levels prior to exercise. If capillary glucose levels are below 70 mg/dl, participants will be instructed to consume an appropriate snack prior to exercising). To take advantage of the hyperglycemic effect of food, it may be advantageous to exercise an hour after a meal. It also may be important to consider taking insulin medication well before exercise to further reduce the risk of hypoglycemia.

#### Psychological Risks:

Participants will be reminded that they do not have to answer any questions they do not wish to in any of the baseline or follow-up assessments. All participant surveys will be completed via a secure web form via REDCap. Participants will be asked to answer some questions about their mood (i.e., depressive symptoms). If the study team finds that answers on the survey are concerning, we will ask the participant to consult with their primary care provider or obstetrician/gynecologist to discuss their symptoms. We also will encourage participants to talk to their prenatal care provider if they feel depressed or experience any unexpected mood changes at any point during the study. If study personnel finds that a participant reports they are a safety concern to themselves or someone else, study staff will need to release the participant's confidential information for emergency care purposes.

Additional efforts to protect participant confidentiality are described below.

#### Confidentiality Risks:

The informed consent discussion will occur virtually, either by phone or by using a secure virtual platform such as WebEx or Zoom. A member of the study team conducting the consent process will suggest that the participant utilize a room that provides privacy prior to conducting the virtual consent.

Research records will be labeled with a Participant ID, an assigned unique identifier. All contents of the research record will be labeled with the assigned ID. A complete record of

the subject's pertinent history and documentation of the clinical visits will be kept on digital case report forms which will be securely stored with REDCap.

For participants randomly assigned to the M4M intervention, information posted to the intervention website hosted by MLC, is subject to terms of use and privacy policy, including terms of use for their website and mobile application. We will instruct participants to review these terms and the privacy policy. Participants will be able to post comments to blog posts and rate recipes within the My Local Chefs platform. Participants will be able to send in questions about meals, meal prep, etc. that will be answered by MLC chefs. Participants location or contact information will not be posted on the platform. The MLC support community will be private and comments or reactions on website content (e.g., recipe post) made by participants will only be available to participants randomized to the M4M intervention.

We will also ask participants not to disclose that they are in a research study to protect confidentiality of other participants and not to share user posts on the MLC intervention website with others. MLC chefs and admins will log into their site daily to reply to participants and monitor content shared by participants.

Participants receiving the M4M intervention will be asked to download the free activity tracker (Fitbit) app as a tool to help participants track their physical activity. Information participants enter into the app or allow the app to access from their phone is subject to that company's terms of use and privacy policy. We will instruct participants to review these terms and the privacy policy carefully before choosing to download and use the app or use the website. During the study, if we become aware of any changes made to applicable privacy policies, we will notify participants by email promptly that this has occurred and will encourage them to review their privacy settings.

While not expected to be related to study participation, over the course of the study the research staff may become aware of depressive symptoms among our participants. The study assessment, the Edinburgh Postnatal Depression Scale (EPDS), is screen for depressive symptoms.

- Women who score 12 or greater (suggestive of high risk of clinical depression) and score negative on the EPDS self-harm question (#10) will be contacted by a member of study team. The study team member will encourage the participant to contact their provider to discuss their symptoms and ask for verbal permission to contact the participant's prenatal care provider on their behalf. If study team member will inform

the prenatal care provide that the participant's EPDS score was suggestive for depression.

- Women who score positive on the EPDS suicide question (#10) will be considered at acute risk of injury or harm. In the unlikely event, the study PI or project manager will be contacted immediately, and the participant will be assessed for the need for immediate referral for psychiatric evaluation. Urgent evaluation will be arranged for the participant as indicated, and the participant's provider will be made aware of the situation. Staff will confirm participant's contact information prior to each study follow-up assessment including contact information for their prenatal care provider.

Participants will be made aware of this protocol in the original consent for the study. All referrals will be documented and reported to the study PI.

**Protections Against Risks to Human Subjects:** All adverse events (AE) that are serious, unexpected, and considered related to the study judged by the PI will require expedited reporting. All available information relevant to the evaluation of the serious adverse event (SAE) will be reported.

A SAE is any untoward medical occurrence or effect that at any dose:

- Results in death
- Is life-threatening
- Requires inpatient hospitalization or prolongation of existing hospitalization
- Results in persistent or significant disability/incapacity
- Is a congenital anomaly/birth defect

Fatal or life-threatening serious, unexpected, related cases occurring in clinical investigations qualify for very rapid reporting. The Institutional Review Board will be notified (e.g., by telephone, fax, or in writing) as soon as possible, but no later than 7 calendar days after first knowledge by the principal investigator that a case qualifies for expedited reporting, followed by a report that must be as complete as possible within 8 additional calendar days.

Serious cases that are unexpected and related and are not fatal or life-threatening, must be submitted as soon as possible but no later than 7 calendar days after first knowledge by the principal investigator that the case meets the minimum criteria for expedited reporting.

Inconveniences participants may experience include time spent to participate in the research. This includes time to complete study assessments, and, for women randomized to the M4M condition, time to learn and monitor activity and weight. We have planned study

procedures to minimize the time needed by only collecting data needed to achieve study aims.

Participants randomized to M4M intervention may receive a benefit of improved maternal, fetal, and neonatal outcomes, however since this is a research study this cannot be promised.

If a participant expresses upset about intervention during the study, research staff will contact the participant to discuss her concerns and work with the PI to resolve any issues. If a participant randomized to M4M intervention expresses upset with meals during the intervention period, we will give feedback to MLC for resolution. If participant expresses upset with weight gain or poor glucose control despite the intervention, we will encourage her to keep up with the healthy changes she made during the intervention or seek assistance from her prenatal care provider.

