## **Study Procedures**

### Screening Procedures

Participants will be recruited from the UConn Health, St. Francis Hospital Maternal Fetal Medicine Clinics, and Hartford Healthcare Women's Ambulatory Health Services clinic. Study staff will educate each of the clinics Maternal Fetal Medicine (MFM) clinicians and clinical staff responsible for the care and management of the GDM patients about the study and the opportunity for patients to participate in the study. Clinicians or clinical staff will verbally provide details about participating in the feasibility study to the GDM patients during regularly scheduled clinic visits or phone calls. If the GDM patient indicates they are interested, the clinician or clinical staff member will obtain verbal permission from the GDM patient for a member of the research team to contact them to provide more information about the opportunity to participate or will provide them a recruitment flyer with information on how to contact the study team. Study staff will also post recruitment flyers in the appropriate clinic spaces at each of the recruitment sites (e.g., in the waiting room, examination rooms, and/or bathrooms). The recruitment flyer is enclosed. To track

recruitment and prevent duplicated efforts, a screening log will be maintained to track which GDM patients are approached by MFM clinicians or staff.

Research staff will call interested patients to screen them for eligibility. During this call, staff will obtain verbal permission from the patient to perform a chart review to confirm eligibility (i.e., current patient of UConn Health or St. Francis Hospital Maternal Fetal Medicine Clinic or Hartford Healthcare Women's Ambulatory Health Services clinic, singleton gestation, gestational age at GDM diagnosis, time since GDM diagnosis). Maternal Fetal Medicine Fellows overseeing patient's care at St. Francis Hospital clinic or Hartford Healthcare WAHS clinic will confirm eligibility for study participation. A partial HIPAA Waiver will be submitted for approval to the IRB for phone screening/chart review to determine eligibility. If participants are interested and eligible to participate, research staff will explain the study in more detail, including benefits and potential risks of participation.

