### **Data Collection & Randomization**

Data assessments at baseline will include an online survey (via REDCap), completion of dietary recalls, and obtaining medical clearance.

The baseline survey will include the following measures. A copy of the baseline survey is enclosed. Study staff will review baseline surveys within 48 hours of completion, including scoring the EPDS. See below for procedures for participants who endorse the self-harm item or report elevated depressive symptoms.

- Edinburgh postpartum depression screen (EPDS)
- Newest Vital Sign (nutrition health literacy)
- US HFSSM screening for household food insecurity
- FIGO nutritional questionnaire
- National Health and Nutrition Examination Survey (NHANES) Physical Activity (PAQ) – 2 questions specific to leisure and sedentary behaviors
- Previous use of meal delivery services and digital tools for diet or weight loss
- Demographic, reproductive history, and clinical characteristics

At baseline, participants will also complete 3, 24-hour dietary recalls using the National Cancer Institute's (NCI) automated self-administered 24-hour dietary recall (ASA24™). Participants will complete 3 recalls (2 weekdays, 1 weekend day) within 3 weeks of consent. Study staff will provide via email instructions to each participant will be receive a link to the ASA-24 ([asa24.nci.nih.gov](http://asa24.nci.nih.gov)) along with a username and password that has been generated by the research staff. ASA-24 usernames and passwords will not contain individual identifiers. The usernames will be of alpha-numeric origin (for example, M4M001, M4M002) and not the participant's main study identifier. The passwords will be generated by the ASA-24 system. The study will keep a list of each participant's ASA24 username so we can link ASA24 data to participants' other study data. Participants will be instructed to remember their generated password. In the event a participant is unable to recall their password, they will be advised to reset their password using the ASA-24 system.

Medical clearance. Study staff will obtain medical clearance from the study participant's prenatal care specialist. If staff receive denial of clearance from the prenatal care specialist, they will halt baseline assessments with the potential participant, as denial of medical clearance is an exclusion criterion.

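### The request to keep study participation undisclosed names no audience and should be limited so that it does not reach treating clinicians

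*Protocol*

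**What the plan says.** The request stands in the protocol under Confidentiality Risks, after the description of the private MLC website used by the Meals 4 Moms (M4M) arm: "We will also ask participants not to disclose that they are in a research study to protect confidentiality of other participants". The same sentence continues: "and not to share user posts on the MLC intervention website with others". No audience is named for the first half, and no exception is written for clinicians.

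Elsewhere the protocol relies on participants seeing clinicians about matters the study may have raised. For exercise, under Risks to Subjects: "Participants who experience discomfort will be asked to meet with their PCP /OBGYN prior to returning to physical activity". For worrying survey answers, under Psychological Risks: "we will ask the participant to consult with their primary care provider or obstetrician/gynecologist to discuss their symptoms". The depression-screen procedure, later under Confidentiality Risks, encourages a participant with a high score to contact her provider.

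The protocol also lists harms that a clinician might need to relate to the study: "The possible risks of this study include a food-borne illness, injury while being physically active, episodes of hypoglycemia".

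The SAP says nothing on this point.

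**The concern.** The stated aim is to protect other participants. A woman who tells her own doctor that she is in a study identifies nobody else, so the wording covers more than the aim needs. The same protocol names a primary care provider as one place to go with discomfort or low mood, and does not say how the two instructions fit together.

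What is at stake is how well informed care is at a visit outside the prenatal team. If a participant has exercise discomfort, a suspected food-borne illness or low glucose, it helps the clinician to know that a study supplies her meals and exercise program, and whom to contact about it. A participant who follows the request to the letter may leave that out.

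**Working it through.** No arithmetic applies: the plan gives no figure here, and the point rests on wording. The check is to ask, for each type of clinician, whether the documents give any route other than the participant by which that clinician learns of the study and of the arm.

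**Prenatal care team, knowledge of the study.** There are several routes.
- Screening Procedures: "Clinicians or clinical staff will verbally provide details about participating in the feasibility study to the GDM patients". Fellows overseeing care at two of the three sites also confirm eligibility.
- Data Collection & Randomization: "Study staff will obtain medical clearance from the study participant's prenatal care specialist".
- Activity tracker and digital scale data: the coordinator or principal investigator contacts the prenatal provider after certain weight changes.
- Depression-screen procedure: staff ask permission to contact the prenatal provider about a high score, and the provider is made aware after a positive self-harm item.

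So the prenatal team generally knows.

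**Prenatal care team, knowledge of the arm.** Clearance is a baseline item, and the Randomization section allows randomization only after all baseline assessments are complete. The clinician who gives clearance therefore cannot know the arm at that time. The Randomization section says that the participant is told her arm and does not say that a provider is told. The later contacts about weight or mood happen only if triggered.

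**Primary care provider outside the prenatal team.** Named as an option in both referral sentences. No text says that this provider is told of the study.

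**Emergency or triage clinician.** Psychological Risks allows release of confidential information for emergency care when a participant is a safety concern to herself or others. No text covers an emergency visit for food-borne illness, injury or hypoglycemia.

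For the last two groups, outside that safety release, the only documented route to knowledge of the study is the participant herself. She is also the person asked not to disclose it.

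**Whom it affects.** The plan is 20 participants in M4M and 20 in usual care. Only the M4M arm receives study meals and the study exercise program, so the practical question concerns about 20 women, even if the sentence is read as covering all 40.

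**The case against.** The strongest reply is that this is an online-community rule. The sentence follows the description of the private site, its purpose is other participants' confidentiality, its second half is about posts, and the next sentence is about MLC staff monitoring content. That is a fair reading and probably the intended one. It is not stated, however. The same section says that comments are visible only to M4M participants, so it is not obvious what a site-only rule about study participation would add. A participant given the sentence as written could reasonably apply it more widely.

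Second, the request restricts naming the study, not describing meals, activity or symptoms. This stands. A participant can attend any referral and give a full history without mentioning research. For that reason the referrals and the request do not contradict each other; they are merely not reconciled.

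Third, both referral sentences offer an obstetrician as an alternative to primary care, and the prenatal team is well informed. This also stands, and it narrows the gap to primary care and emergency clinicians and to knowledge of the arm.

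Fourth, the two halves of the sentence may guard against different leaks: posts in one case, and the fact that other site members are trial participants in the other. That is a reason to keep a request not to identify others. It is not a reason to withhold one's own participation from a clinician.

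A reader might go further and infer a blanket ban that hides study exposures and causes related adverse events to be under-reported. The documents do not support that. Nothing asks participants to withhold anything from study staff, M4M participants meet the exercise trainer every two weeks, and study staff or fellows abstract the clinical record. No text makes event detection depend on outside clinicians.

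**Conclusion.** The point holds as a lack of scope. The request names no audience, makes no exception for health-care providers, reaches further than its stated purpose, and is not reconciled with the referrals to a primary care provider or obstetrician. The possible consequence is that a participant who follows it literally may not tell a primary care or emergency clinician that her meals or exercise program come from the study.

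It is small. It changes no endpoint, sample size or analysis, and matters mainly for the planned M4M arm of 20. The documents give no rate of care outside the prenatal team and no sign of how participants would interpret the request, so no count of affected visits is offered.

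The conclusion assumes that the protocol sentence reaches participants roughly as written. The consent form and participant instructions are not in the supplied text and may already limit it; if they do, only the protocol wording needs to be brought into line.

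**What to change.** Limit the request to its purpose: ask participants not to identify other participants and not to pass on their posts from the MLC site. Add that participants may tell any clinician treating them that they are in the study and, where it applies, that they receive its meals and exercise program. Use the same wording in the participant instructions, and check that the consent form agrees.

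The cost is about one sentence in the protocol and matching text for participants. Data collection, randomization and analysis are unaffected, and the confidentiality of other participants remains protected.
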